**Post Myocardial Infarction Risk Stratification for Sudden Cardiac Death in Patients
with Preserved Ejection Fraction (PRESERVE EF) Study**

Clinicaltrials.gov identifier: NCT02124018

January 23rd 2019

Methods

Trial oversight: The PRESERVE EF study is a multicenter, prospective, observational cohort study (clinicaltrials.gov identifier NCT02124018) with seven Cardiology departments in Greece actively participating. Study protocol was approved by all institutions' ethics committees and was endorsed by the Hellenic Society of Cardiology with an anonymized online database created and maintained in its servers(1).

Patients: Post-angiographically proven MI patients, at least 40 days after the event (90 days after surgery if they underwent coronary artery bypass grafting)(2, 3), with LVEF \geq 40% (also assessed after 40 or 90 days, respectively from the index event), either revascularized or not – but without any evidence of active ischemia (following negative myocardial scintigraphy/exercise treadmill test/stress echocardiography in the previous 6 months), on optimal tolerated medical therapy, were enrolled. Exclusion criteria were: (1) Presence of a secondary prevention indication for ICD implantation, (2) Presence of a permanent pacemaker, due to potential effects on NIRF acquisition following pacemaker dependency and cardiac memory(4), (3) Persistent, long-standing persistent and permanent atrial fibrillation, (4) Neurological symptoms (presyncope or syncope) within the last 6 months, (5) Patients with systemic illnesses (cancer, liver failure, end-stage renal disease, rheumatic diseases and thyroid dysfunction), (6) Administration of antiarrhythmic medication other than β -blockers, (7) Age \geq 80 or \leq 18 years old.

All patients provided written informed consent.

Study protocol: A two-step stratification algorithm was implemented(1). Upon the first step of the algorithm, an ambulatory 24-hour, as well as signal-averaged electrocardiogram recordings were obtained and evaluated for the presence of the following NIRFs(1, 5-8): (1) >30 premature ventricular complexes/hour on 24-hour electrocardiography, (2) presence of non-sustained ventricular tachycardia on 24-hour electrocardiography, (3) 2/3 positive criteria for late potentials, either conventional or modified(8), (4) QTc derived from 24-hour electrocardiography >440 ms (men) or >450 ms (women)(6) according to the Fridericia formula from a signal recorded in 3 pseudo-orthogonal leads, (5) Ambulatory T-wave alternans $\geq 65\mu$ V in two Holter channels(5), (6) Standard deviation of normal RR intervals ≤ 75 ms on the 24-hour electrocardiography, (7) Deceleration capacity ≤ 4.5 ms and heart rate turbulence onset $\geq 0\%$ and heart rate turbulence slope ≤ 2.5 ms(7).

In the presence of at least one NIRF, patients underwent invasive PVS and were classified as inducible if sustained monomorphic ventricular tachycardia or ventricular flutter or polymorphic ventricular tachycardia were induced. The arrhythmia induced was defined as sustained monomorphic ventricular tachycardia when a uniform morphology of QRS complexes with a rate between 120-220bpm was observed, while persisting for ≥ 30 seconds (or shorter, if termination was necessary due to hemodynamic instability). Faster rates of regular monomorphic ventricular tachycardia (≥ 220 bpm) not permitting QRS complexes to be readily distinguished from T waves and without deterioration towards fibrillation, were defined as ventricular flutter, but they were included in the monomorphic category. Polymorphic ventricular tachycardia was defined if constantly changing morphologies and axis were present, eventually degenerating into fibrillation. See “Appendix” for PVS protocol details.

Patients with paroxysmal atrial fibrillation were evaluated for NIRF presence and submitted to PVS while on sinus, with same stimulation protocol implemented in all cases.

Risk level groups: After completion of the study protocol, patients were stratified into three groups:

- Group 1 – No NIRFs present – no invasive PVS performed
- Group 2 – At least one NIRF present – noninducible upon PVS
- Group 3 – At least one NIRF present AND inducible upon PVS.

An ICD was offered only to Group 3 patients.

Patients declining PVS were considered not to have completed stratification and were not included in the protocol performance and survival analyses, yet were followed up as scheduled for the occurrence of any events. Patients completing the protocol but declining an offered ICD were fully included in all analyses.

ICD programming: In accordance with trials favouring prolonged detection intervals at higher rates for the avoidance of treatment of self-terminating arrhythmic events(9), ventricular tachycardia therapy cycle length was set to 330msec and number of intervals to detect to 32. Fibrillation therapy cycle length was set to 270msec and number of intervals to detect to 18/24. In devices with time programming, the same cycle lengths were used but intervals were set to 7sec for CLs in the 270-330msec range and to 2.5sec for CLs<270msec.

Ventricular tachycardia therapy consisted of several attempts of antitachycardia pacing, followed by cardioversion at progressively increasing energy. High-energy shocks were administered to terminate ventricular fibrillation. In 32 cases dual-chamber ICDs were inserted, while in the remaining 5 a single-chamber device was chosen by both the primary and implanting physicians, after excluding the presence of bradyarrhythmic aberration on the electrophysiological study.

Follow up: Implanted patients were followed up every three months, and nonimplanted patients every six months. Events included cardiac (sudden and nonsudden) and non-cardiac death. Acute coronary syndromes and/or repeat revascularization events were also recorded. All device activation were adjudicated independently by two electrophysiologists ([name] and [name]). In case of discrepancy, a third electrophysiologist ([name]) reviewed the event.

Outcomes: The primary endpoint of the study was the occurrence of MAEs, namely either SCD/clinical ventricular tachycardia/fibrillation or/and appropriate ICD activation. SCD was defined as death occurring within one hour of symptom onset if no evidence of alternative causes was present. Death was considered nonsudden cardiac if occurring in the context of heart failure deterioration. All other deaths were classified as noncardiac. The secondary endpoint was total mortality.

Statistics: The primary goal of the study was to assess the proposed two-step PVS-inclusive risk stratification algorithm's ability to identify a subpopulation of post-myocardial infarction patients with left ventricular ejection fraction $\geq 40\%$ at risk for MAEs. To that end, the study was designed to have a statistical power of 80% for detecting free from primary endpoint occurrence survival curve divergence at the 0.05 significance level(1). All continuous variables were checked for normality of distribution, using the Shapiro-Wilk test. Regarding those with normal distribution, Student's t-test was used for all comparisons. In case of non-normality, the Mann-Whitney U-test was used. In cases of categorical variables Fisher's exact test was used. Binary logistic regression was used to compare the odds ratio between groups with different number of NIRFs regarding inducibility. Kaplan-Meier curves were used to visualize survival free from primary endpoint occurrence and the logrank test was applied to assess the presence of statistically significant differences. A two-sided p-value of ≤ 0.05 was considered statistically significant in all cases.

Power analysis(1): Due to the paucity of data regarding PVS yield in similar population cohorts, it was necessary to use metrics derived from noninvasive indices included in this Study as well. After setting the type I error probability for a two sided test at 5% and the power of our study at 80%, SDNN was found to be the variable that required the largest sample (a ratio of high SDNN patients/controls to low SDNN patients/exposed equal to 12 was anticipated). The anticipated accrual/mean follow up intervals were 2 and 3 years, respectively. Relative risk (based on SDNN performance) of control subjects relative to exposed subjects was equal to 0.65. Based on the above, 66 exposed subjects and 792 control subjects would need to be studied to be able to reject with a probability of 80% the null hypothesis that the exposed and control survival curves are equal.

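### Only Group 3 is offered the ICD that can record one component of the primary endpoint, and the plan states no reporting by component that would separate higher risk from better detection

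*Combined protocol and SAP*

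**What the plan says.** All references are to the run-in headings of the combined protocol and SAP.

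- **Outcomes:** "The primary endpoint of the study was the occurrence of MAEs, namely either SCD/clinical ventricular tachycardia/fibrillation or/and appropriate ICD activation". Also: "The secondary endpoint was total mortality".
- **Risk level groups:** Group 3 is the patients with at least one noninvasive risk factor who are inducible at programmed stimulation. "An ICD was offered only to Group 3 patients". On refusals: "Patients completing the protocol but declining an offered ICD were fully included in all analyses". The number who declined is not given.
- **ICD programming:** "ventricular tachycardia therapy cycle length was set to 330msec and number of intervals to detect to 32"; for devices programmed by time, "intervals were set to 7sec for CLs in the 270-330msec range". "Ventricular tachycardia therapy consisted of several attempts of antitachycardia pacing, followed by cardioversion at progressively increasing energy". There were 32 dual-chamber and 5 single-chamber devices.
- **Follow up:** visits are three-monthly for implanted patients and six-monthly for the others. Two electrophysiologists, with a third for disagreements, adjudicate device activations. No adjudication is described for clinical arrhythmias or deaths.
- **Statistics:** Kaplan-Meier curves and a logrank test on the whole composite. The groups entering the logrank are not named, and neither reporting by component nor a sensitivity analysis is stated. The section refers the design and power to a published design paper, which was not available for this review.

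**The concern.** The study's main aim is to show that the two-step algorithm picks out patients at risk of major arrhythmic events (MAEs). Group 3 is the group the algorithm calls high risk, and it is the only group offered a device that detects, treats and stores arrhythmias. Sudden death can be counted in every group. An arrhythmia that a device ends by pacing can be counted only in an implanted patient. The same arrhythmia in Group 1 or 2 counts only if it comes to attention as clinical tachycardia or fibrillation, and the plan does not say how long that must last or how it is to be found.

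More frequent visits and an adjudication process tied to devices add to the difference. If the curves separate on this composite alone, a reader cannot tell how much is a true difference in risk and how much is a difference in recording. The plan as written would credit both to the algorithm.

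**Working it through.** **1. What can be recorded, by patient type**

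| | Implanted (Group 3) | Groups 1 and 2, and Group 3 decliners |
|---|---|---|
| Sudden cardiac death | counts | counts |
| Clinical VT/VF | counts | counts if it surfaces; duration and method not stated |
| Appropriate ICD activation | counts, adjudicated | cannot occur |
| Scheduled visits | every 3 months | every 6 months |

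**2. How little is needed for a device to act.** 60,000 / 330 = 182 bpm is the rate at the edge of the tachycardia zone. At that rate, 32 x 330 ms = 10.56 s to detection; with time programming it is 7 s. Therapy begins with pacing, and the endpoint's activation is not limited to shocks.

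**3. Inputs for an illustration.** From the documents: implanted 32 + 5 = 37; planned total 66 + 792 = 858 (derived for SDNN; the analysed number is not given); two years' accrual and three years' mean follow-up; two-sided 0.05. Assumed: the same true event hazard in everyone, 1, 2, 3 or 6% per year; no decliners; Group 3 against all others (37 v 821); follow-up uniform between 2 and 4 years; and a share f of events that surface without a device. This f is applied to the whole composite, sudden death included.

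The ratio of recorded rates, implanted to others, is then about 1/f: 1.11 for f = 0.9, 1.33 for f = 0.75 and 2 for f = 0.5. Expected events in implanted patients are 37 x (1 - exp(-3 x hazard)): 37 x (1 - exp(-0.03)) = 1.1 at 1%, and 37 x (1 - exp(-0.18)) = 6.1 at 6%.

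**4. Proportion of runs in which the logrank rejects in favour of Group 3** (4,000 runs per cell)

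| f | 1%/yr | 2%/yr | 3%/yr | 6%/yr |
|---|---|---|---|---|
| 1 (equal detection) | 4.7% | 4.8% | 4.2% | 3.4% |
| 0.9 | 6.6% | 6.1% | 6.0% | 6.2% |
| 0.75 | 8.6% | 10.1% | 11.2% | 15.2% |
| 0.5 | 16.6% | 23.0% | 26.7% | 40.0% |

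Repeat runs agree within simulation error; at f = 0.9 they span 5-7%.

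The first row is already above the 2.5% expected in one direction because 37 v 821 is so unbalanced with few events. That part is not a device effect. The device effect is the rise from the first row.

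**5. Cross-check by a different route.** If non-implanted patients have a recorded rate of 1% per year and implanted patients twice that, the two-sided rejection rate is 24%. That matches f = 0.5 at a true 2% per year (23.0%).

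**6. Sensitivity to the set-up**

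- With 20 decliners in Group 3 (assumed), the four rows become 3-4%, 5-6%, 7-10% and 14-29%.
- With 500 patients instead of 858, they become 3-4%, 6%, 9-13% and 17-38%.
- With a three-group logrank (410/411/37 assumed) at 1, 2 and 6% per year, any rejection occurs in 8, 9 and 11% of runs at f = 0.75, and in 15, 20 and 34% at f = 0.5.

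**The case against.** Several points against the concern have force.

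- **The detection settings are deliberately long.** The plan says they aim to avoid treating self-terminating arrhythmias. Tachycardia slower than 182 bpm lies outside the therapy zone, and only appropriate activations count. This reduces the asymmetry without removing it.
- **ICD activation belongs in the composite.** A device may abort an event that would otherwise have been a death or a clinical arrhythmia. This stands, and it is why the composite should remain primary.
- **Decliners stay in Group 3.** This dilutes the effect, as the figures show, but their number is unknown.
- **Total mortality needs no device to be counted.** It is secondary, ICD treatment may affect it, and it does not isolate the device-recorded share.
- **The design paper may plan a breakdown.** It may. The point is limited to the supplied document.
- **The illustration is generous to the concern.** Sudden death surfaces without a device. If it were 20% of true events (assumed), f = 0.5 overall would need only (0.5 - 0.2) / 0.8 = 37.5% of the remaining events to surface. If arrhythmias recur, fewer patients than episodes are missed. Both objections stand, and f = 0.5 should be read as an extreme case.

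A reader might also set the 10.6 s detection time against the 30 s in the Study protocol section ("while persisting for ≥ 30 seconds (or shorter, if termination was necessary due to hemodynamic instability") and infer that the endpoint applies different duration thresholds by group. The documents do not support that. The 30 s defines tachycardia induced at programmed stimulation, allows shorter episodes with instability, and is not an endpoint rule. The supportable point is only that clinical tachycardia has no stated duration.

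**Conclusion.** The structural problem is certain on the text. One component of the primary composite can be recorded only in implanted patients, the offer of implantation is restricted to the group under test, and the supplied plan analyses only the total. Visit frequency and adjudication differ in the same direction.

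The size is unknown. With equal true risk, the chance of a result falsely favouring Group 3 rises from 3-5% to 5-7% if 9/10 of events surface without a device, to 9-15% if 3/4 do, and to 17-40% in the extreme case of half. These figures rest on assumed hazards, surfacing shares and grouping, on no decliners, and on a planned rather than analysed total. They show that the question can matter, not that it did.

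A reader might infer that any divergence would be a device artefact, or that the composite is invalid. Neither follows: sudden death and clinical arrhythmia can be counted in every group, and nothing in the documents shows that events were missed. What holds is that a difference on the composite alone cannot be divided between risk and detection. This should be fixed; confidence in its practical importance is medium.

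**What to change.** 1. Keep the composite as the primary endpoint.
2. Report first MAEs by component (sudden cardiac death, clinical VT/VF, ICD activation only) for each risk group. Split Group 3 descriptively into implanted and ICD-declined, noting that decliners are self-selected.
3. State in the conclusion that divergence driven by ICD-only events cannot be attributed to higher risk alone.
4. Optional: a Kaplan-Meier and logrank analysis leaving out ICD-only events. Label it as biased against the algorithm, because ICD therapy can abort events that would otherwise have surfaced, and attach no decision rule. It does not remove the differences in visit frequency or adjudication.
5. Label these analyses post hoc if they are added after the data have been reviewed.

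Item 4 is optional because it says little. Suppose a true hazard ratio of 2, with a quarter of implanted patients' events surfacing clinically (both assumed). Group 3 then shows no excess in 53-80% of runs without decliners and in 28-52% with 20. At 1% per year without decliners, the chance of no counted event in Group 3 is about (1 - 0.25 x (1 - exp(-0.06)))^37 = 58%.

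The cost is wording and re-tabulation of events already recorded, with no new visit or procedure. The downside is few events per component (perhaps 1 to 6 composite events among implanted patients under equal risk at 1-6% per year) and a more cautious conclusion.

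### The death rule labels fatal reinfarction without heart failure as noncardiac, and only the sudden-death limb of the primary endpoint excludes alternative causes, a term left undefined

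*Combined protocol and SAP*

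**What the plan says.** Under Outcomes, the primary endpoint is the MAE, "namely either SCD/clinical ventricular tachycardia/fibrillation or/and appropriate ICD activation". The first limb has a condition attached: "SCD was defined as death occurring within one hour of symptom onset if no evidence of alternative causes was present". The clinical arrhythmia limb and the device limb have no such condition, and the document does not say what an alternative cause is.

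The remaining deaths are divided in two steps: "Death was considered nonsudden cardiac if occurring in the context of heart failure deterioration. All other deaths were classified as noncardiac".

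Follow up lists sudden cardiac, nonsudden cardiac and noncardiac death among the events. It adds: "Acute coronary syndromes and/or repeat revascularization events were also recorded". Independent double review is described there for device activations, but not for deaths or clinical arrhythmias.

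Three other places matter. Patients enter "without any evidence of active ischemia" (Patients). ICDs were offered to Group 3 alone (Risk level groups). The main comparison is a Kaplan-Meier and logrank analysis of freedom from the primary endpoint (Statistics). The secondary endpoint is total mortality (Outcomes). No stated analysis uses the recorded ACS events.

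**The concern.** Every participant has had a proven infarction, and the plan expects new coronary events enough to record them. Yet the death categories have no place for a fatal coronary event that is neither sudden nor due to heart failure. By default it becomes noncardiac, so any table of deaths by cause would understate cardiac death.

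The primary endpoint raises a related question. If ventricular arrhythmia arises during a new ACS, two limbs count it whatever the trigger, while the SCD limb may not. A device can record and treat an arrhythmia that would otherwise leave only a death without a rhythm strip. Devices are concentrated in the group the algorithm marks as high risk. If such events occurred, uneven counting would act on the curves that the logrank test compares, and would tend to widen their separation.

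There is also a question of interpretation. Patients were free of active ischaemia at entry, so a reader will want to know whether the curves still diverge once arrhythmias linked to a later coronary event are set aside.

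**Working it through.** The plan gives no figure on this point, so the check applies its written definitions to each way an ACS can end.

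**Inputs (Outcomes)**
- SCD: death within one hour of symptoms and no evidence of an alternative cause.
- Clinical VT/VF: no condition on trigger, and none on survival.
- Appropriate ICD activation: no condition on trigger.
- Nonsudden cardiac death: heart failure deterioration only.
- Noncardiac death: everything else.

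| ACS-related event | Death label | MAE? |
|---|---|---|
| VT/VF, survived or treated by an ICD | none | Yes |
| Death with documented VT/VF | by timing and cause | Yes, through the clinical VT/VF limb |
| Death within one hour, no evidence of ACS or other cause | SCD | Yes |
| Death within one hour, ACS documented, no heart failure deterioration, no rhythm recorded | SCD or noncardiac | Depends on whether ACS is an alternative cause |
| Death after one hour, no heart failure deterioration, no rhythm recorded | Noncardiac | No |
| Death after one hour in heart failure deterioration, no rhythm recorded | Nonsudden cardiac | No |

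**Reading the table**
1. The fifth row needs no interpretation. A late death from a documented reinfarction, without heart failure deterioration, is labelled noncardiac by the stated rule. The same holds for a non-SCD death from coronary revascularization.
2. The fourth row is undetermined. If documented ACS is an alternative cause, the death is not SCD, not an MAE, and is labelled noncardiac. If it is not, the death is SCD and an MAE.
3. Rows one and four together give the possible unevenness in the primary endpoint. Device-treated VT/VF in an ACS counts, while a death within one hour in an ACS with no recorded rhythm may not.

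**Scale**
- ICD programming reports 32 dual-chamber and 5 single-chamber devices: 32 + 5 = 37.
- If all went to Group 3, that group has at least 37 patients, since those who declined a device stay in the analyses.
- One patient whose only MAE was a device-treated ACS-related arrhythmia would add at most 1/37 = 0.027, or 2.7 percentage points, to Group 3's crude MAE proportion.
- One fourth-row death in Group 1 or 2 adds either one event or none. The sizes of those groups are not given.

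This shows what one event weighs. It does not estimate bias. The Power analysis gives a relative risk of 0.65 and 66 exposed with 792 control subjects, but no MAE rate, so an expected event count cannot be derived from it either.

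**The case against.** The strongest reply is that the part that is certain reaches no stated analysis. Labels cannot change total mortality, the primary endpoint uses only the SCD category, and no cause-specific mortality analysis is specified. That stands. It limits the labelling fault to the descriptive split of deaths, which the study nevertheless lists as events.

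A reader might infer more: that the same ACS-provoked arrhythmia is a primary event if survived and a noncardiac death if fatal. The documents do not support this. The clinical VT/VF limb has no survival condition, so a fatal ACS with documented VT/VF is an MAE whatever the death label. Sudden death without evidence of ACS is SCD. Late ACS death in heart failure deterioration is nonsudden cardiac. For a death within one hour with documented ACS, the outcome turns on an undefined term.

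A reader might also try to state the share of primary events affected. Assuming 5 to 20 MAEs, of which 1 to 3 are ACS-related, gives 1/20 = 5% to 3/5 = 60%. That range reflects only the assumed counts. It also measures events already in the endpoint, whereas the deaths in question are those that may be missing from it.

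Three further objections have weight. Some ACS deaths without a recorded rhythm are not arrhythmic, so leaving them out of an arrhythmic endpoint is not necessarily wrong. Better arrhythmia detection in patients with devices is a general feature of the design and not peculiar to ACS. And the stated goal is to identify patients at risk of MAEs, without restriction to events from the baseline substrate. These points argue for a sensitivity analysis and against replacing the primary one.

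**Conclusion.** Two conclusions follow, with different certainty.

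The death rule is wrong as written. It assigns to noncardiac a class of deaths that are plainly cardiac: those from documented ACS or coronary revascularization that are not SCD and occur without heart failure deterioration. This rests on the text alone. It affects the cardiac and noncardiac event categories in every group and leaves total mortality unchanged.

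The primary endpoint has an unresolved boundary. One of its three limbs carries an undefined exclusion and the other two carry none. Deaths within one hour with documented ACS and no recorded rhythm may be omitted while device-treated arrhythmia in the same setting is counted, and this could differ by group because only Group 3 was offered a device. Whether it did depends on how alternative causes were read and on whether such events occurred. The documents report neither, so its size cannot be computed, and they do not show that the primary comparison is biased. Both parts merit correction because the remedy is cheap.

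**What to change.** 1. In Outcomes, class a death from documented acute infarction or other ACS, or from coronary revascularization, as nonsudden cardiac whenever it does not meet the SCD definition. Keep noncardiac for deaths without a cardiac cause.

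2. State whether documented ACS is an alternative cause for SCD.

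3. Using the recorded ACS events, flag as ACS-related, in every group: SCDs, deaths within one hour of symptom onset with evidence of ACS, clinical VT/VF, and appropriate ICD activations. Set a time window for the link if the recorded dates allow. The within-one-hour deaths need their own place in this list. Otherwise step 1 could move them out of SCD and they would escape the flag, which would preserve the unevenness.

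4. Repeat the Kaplan-Meier and logrank analysis twice as a sensitivity analysis. In one run, count all flagged events as MAEs in every group, including the within-one-hour ACS deaths. In the other, count none of them and censor the patient at the event in every group.

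The cost is a few sentences in Outcomes, a review of recorded events, and two extra runs. It assumes that the ACS records hold enough detail to link events. The second run has fewer events and its censoring may be informative. The document already reports the devices inserted, so if event data are known, these analyses should be labelled post hoc.

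### Minor: the pooled-variance t-test for normal variables does not hold its 5% error if the groups differ in both size and spread; Welch's test would

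*Combined protocol and SAP*

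**What the plan says.** The Statistics paragraph sets one rule for continuous variables. First, "All continuous variables were checked for normality of distribution, using the Shapiro-Wilk test". For those that pass, Student's "t-test was used for all comparisons. In case of non-normality, the Mann-Whitney U-test was used". No check of equal variances and no unequal-variance version of the t-test appears. The same paragraph adds: "A two-sided p-value of ≤ 0.05 was considered statistically significant in all cases".

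Three other places bear on group size:

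- Power analysis: "a ratio of high SDNN patients/controls to low SDNN patients/exposed equal to 12 was anticipated", leading to "66 exposed subjects and 792 control subjects would need to be studied".
- Risk level groups: three groups, beginning with "Group 1 – No NIRFs present – no invasive PVS performed". Group 3 has at least one NIRF and is inducible, and it is the only group offered an ICD.
- ICD programming: 32 dual-chamber and 5 single-chamber devices were inserted.

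The document does not list which pairs of groups are compared by t-test, how large those groups are, or any SD.

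**The concern.** Without a qualifier, Student's t-test means the pooled-variance test, and nothing in the text points to Welch's version. Its standard error is right if the two groups share one variance, and nearly right in balanced groups even if they do not. When one group is much smaller, the pooled variance mostly reflects the larger group, while most of the uncertainty in the mean difference comes from the smaller one. If the smaller group is more variable, p-values come out too small; if it is less variable, too large. A Shapiro-Wilk test gives no warning of either.

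At stake is the stated 5% error of comparisons of continuous characteristics, for example between risk groups or between inducible and noninducible patients.

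**Working it through.** **Inputs from the document.** Two-sided 0.05 (Statistics); 12 × 66 = 792, total 858 (Power analysis); 32 + 5 = 37 ICDs (ICD programming). Because ICDs were offered only to Group 3 and some patients may have declined, Group 3 has at least 37 patients.

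**Assumed inputs.** SD ratios *r* (smaller group / larger group) from 0.8 to 1.5, and a comparison group of 100 as an example of milder imbalance. The document gives neither.

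**The plan's own figure.** The 66/792 sample size cannot be reproduced, because no event rate or median event-free time is stated for controls. With a relative risk of 0.65, 2 years of accrual and 3 years of follow-up, it is reached if the control median is about 3.4 years. It is a survival calculation and serves here only as an example of a 12:1 split.

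**Formula.** With equal means, the larger group's SD set to 1, n₁ the smaller group and n₂ the larger:

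- true variance of the difference: T = r²/n₁ + 1/n₂
- variance Student's test uses, on average: S = [((n₁−1)r² + (n₂−1)) / (n₁+n₂−2)] × (1/n₁ + 1/n₂)
- large-sample true error: 2 × [1 − Φ(1.96 × √(S/T))]

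At 66 vs 792 the larger group has 791/856 = 92% of the weight in the pooled variance. With equal SDs, the smaller group contributes (1/66)/(1/66 + 1/792) = 92% of the variance of the difference. That mismatch is the mechanism.

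**Worked cases.**

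- 66 vs 792, r = 1.5: T = 2.25/66 + 1/792 = 0.03535. S = [(65 × 2.25 + 791)/856] × 0.016414 = 1.0949 × 0.016414 = 0.01797. √(S/T) = 0.713; 1.96 × 0.713 = 1.397; error = 16.2%.
- 66 vs 792, r = 0.8: T = 0.01096, S = 0.9727 × 0.016414 = 0.01597, √(S/T) = 1.207, error = 1.8%.
- 37 vs 100, r = 1.5: T = 2.25/37 + 1/100 = 0.07081. S = [(36 × 2.25 + 99)/135] × 0.037027 = 1.3333 × 0.037027 = 0.04937. √(S/T) = 0.835, error = 10.2%.

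**Simulation.** 200,000 runs per setting, normal data, equal means, nominal 5%:

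| Sizes | r | Student | Welch |
|---|---|---|---|
| 66 vs 792 | 0.8 | 1.9% | 5.1% |
| 66 vs 792 | 1 | 5.0% | 5.0% |
| 66 vs 792 | 1.25 | 10.4% | 5.0% |
| 66 vs 792 | 1.5 | 16.2% | 5.1% |
| 37 vs 100 | 0.8 | 3.0% | 5.0% |
| 37 vs 100 | 1 | 5.0% | 5.1% |
| 37 vs 100 | 1.25 | 7.6% | 5.0% |
| 37 vs 100 | 1.5 | 10.1% | 4.9% |
| 429 vs 429 | 1.5 | 5.1% | 5.1% |

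The last row shows that unequal spread alone does no harm; it needs unequal size as well.

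**Price of Welch when variances are equal** (true difference 0.5 SD, assumed sizes): at 37 vs 792, power is 84.0% for Student and 82.3% for Welch, a loss of 1.7 points. At 66 vs 792 it is 97.4% and 97.1%, a loss of 0.3 points.

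**The case against.** The strongest reply is that the simulated settings may not describe this study. Most of it stands.

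- **Sizes.** A reader might take 12:1 as the split of the t-test comparisons. It is the low- vs high-SDNN split in a survival power calculation. Inducible vs noninducible is a comparison within NIRF-positive patients, and its imbalance is not stated. Marked imbalance is probable but not documented.
- **Spread.** A reader might infer that unequal spread is built in, because Group 1 is cut off at the NIRF thresholds. A normal variable truncated at +1 SD does have its SD reduced to 0.79. But Shapiro-Wilk rejects normality for such a variable in 99% of samples at n = 150 and in 100% at n = 300 to 792, so if normality is checked by group it goes to Mann-Whitney. Truncation at +2 SD is detected less often (20% at n = 150), but the SD is then 0.94, a ratio of only about 1.06. The means of these measures also differ by the grouping rule itself (a shift of −0.29 SD at +1 SD), so a type I error rate has little meaning there. For variables not used in the grouping, such as age or LVEF, the document gives no reason to expect different SDs.
- **Consequence.** A reader might fear for the main result. The primary endpoint is analysed by Kaplan-Meier and logrank, inducibility by number of NIRFs uses logistic regression, and total mortality is an event endpoint. None of these rests on a t-test.
- **Small departures.** At an SD ratio of 1.1 the error is only about 7% at 66 vs 792 and 6% at 37 vs 100.

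What the reply does not remove is that the plan relies on an assumption it neither states nor checks, although a test that does not need it is available at almost no cost.

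**Conclusion.** The point holds as a minor one. The plan names the pooled-variance test and checks only normality. If group sizes and SDs both differ, the nominal 5% error of these ancillary comparisons is not held, and it can move in either direction. For SD ratios of 0.8 to 1.5 it is about 2% to 16% at 66 vs 792 and about 3% to 10% at 37 vs 100. These ranges rest on assumed SD ratios, on normal data and on group sizes that the document does not give for any t-test; at a ratio of 1 there is no distortion.

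The document does not support saying that the p-values are wrong, only that they could be. Nor does the defect require giving up the Shapiro-Wilk step: how to choose between a t-test and Mann-Whitney is a separate and debatable question.

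**What to change.** In the Statistics paragraph, replace Student's t-test by Welch's unequal-variance t-test for comparisons of means, and report each mean difference with its Welch 95% CI. No preliminary test of variances is needed, and the rest of the paragraph can stay. If Welch's version was already meant, naming it settles the matter.

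The cost is one sentence and one software option, or a re-run if the comparisons have already been made, as the past tense suggests. Sample size, data collection and the primary analysis do not change. The downside is the loss of about 0.3 to 2 points of power where variances are in fact equal.
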